11.1 Data Collection Management

All assessments and data collections are to be conducted according to the Schedule of Evaluations in Appendix II. Medical record abstraction for current diagnoses and medications should include all data since the participant's last AMP Up visit, and must be completed within 3 months after completion of the ASTRO Standalone Study visit.

For YAPHIV, current HIV disease data (HIV viral load and CD4 T cell count and percent) from within the 3 months prior to the visit should be collected from the participant's AMP Up study record or clinical record. If not available, sites will perform the tests as part of the ASTRO Standalone Study. According to Human Subjects Protection guidelines, a participant may voluntarily decline any specific protocol assessment or specimen collection during a study visit, and any such missed assessments will not be considered a protocol deviation. Thus, voluntary participant refusal of any research activities does not require HLC IRB notification. The site should document the participant's decline of a specific protocol assessment or specimen collection in the participant's file and on the appropriate CRF.

11.2 Enrollment of Participants with Cognitive Impairment

Potential participants with cognitive impairment who meet study eligibility criteria will not be excluded from enrollment. Enrollment of participants with cognitive impairment is justified given that the cause of the cognitive impairment may be related to the exposures being studied and not enrolling these individuals may introduce bias into the study. The ASTRO Standalone Study is an observational study; therefore, any potential risks or negative impacts on the well-being of these individuals are minimal. Given these conditions, enrollment of participants with cognitive impairment is in line with the U.S. Department of Health and Human Services (DHHS) and FDA regulations.

However, potential participants with significant cognitive impairments that would render them unable to complete study assessments (as determined by the clinical site PI or designee) should not be enrolled in the studies. Site staff should consult with the Protocol Team through the QNS if they have any concerns regarding a participant's eligibility for a study.

Participants with cognitive impairment will consent on their own behalf if legally able. For individuals with a LAR, LAR permission and participant assent will be obtained. Participating sites will consult with the HLC IRB, or site IRBs if indicated, for guidance when needed. Caregivers of participants with cognitive impairment may answer questions as proxies on behalf of participants but will not be consented and enrolled as study participants themselves.

11.3 Discontinuing Study Participation

Participants will be discontinued from the ASTRO Standalone Study if any of the following occurs:

- The participant withdraws permission;
- The participant fails to comply with the study requirements so as to cause harm to self or seriously interfere with the validity of the study results and the clinical site PI believes that compliance is unlikely to improve;

- The clinical site PI determines that further participation would be detrimental to the participant's health or well-being;
- The study is stopped by a governmental agency, including the NIH or DHHS;
- The clinical site is terminated for significant participant safety concerns, study integrity, poor performance issues, or lack of funding; or
- The HLC IRB decides to withdraw approval for the study due to participant safety concerns.

11.4 Participant Compensation

As approved by the HLC IRB, participants enrolled in the ASTRO Standalone Study will receive \$65 for their time and effort in the completion of study procedures and assessments.

12. Adverse Event (AE) Reporting

The ASTRO Standalone Study is not a therapeutic study and no medications are prescribed or given as part of this study. Young adults enrolled in this study may develop common conditions requiring treatment during the course of the study period. Site study personnel will assist the participants in receiving appropriate care as appropriate to their roles at their site. YAPHIV participants may also experience AEs associated with HIV infection, ART exposure, or other medications. Clinical site PIs are encouraged to use the FDA's MedWatch system to report any events possibly associated with medications clinically prescribed for the participant.

13. Study Impact and Safety Monitoring

The Protocol Teams will monitor participant-, staff-, and community-associated untoward events. Monitoring will consider the impact of the study on the welfare of three groups of people:

- Research participants.
- Site research staff.
- The community in which the research is being conducted.

Reporting of participant or staff-associated negative study impact events to the Protocol Team will result in the re-examination of study procedures and allow changes as necessary to address concerns about participant management, recruitment, enrollment, adequacy of training, and/or the need to modify procedures. Community-associated untoward event reporting will facilitate understanding of the impact of the study on the community and will provide the opportunity to address community-level concerns and to intervene in a timely manner to correct misinformation or perceptions of practices that may cause community concern.

All clinical sites have psychologists, social workers, or other clinical staff qualified to address situations if a participant becomes distressed. In addition, PHACS has developed the PHACS Emergency Procedures for sites to follow in these circumstances (available on the PHACS website at <https://my.phacsstudy.org> within the PHACS Manual of Network Policies and Procedures).

13.1 Grading of Impact

The grading system for events involving study participants or staff will be as follows:

- Minimal Impact: managed at the time of event with no consequences.
- Moderate Impact: managed by referral for supplemental care/counseling.
- Major Impact: needed immediate professional intervention with or without hospitalization.

Community events will not be graded but will be addressed as they occur.

13.2 Reporting Requirements

All moderate and major impact events involving study participants or staff are to be reported to the Protocol Team through the QNS by the clinical site. Any event that is deemed to have negatively impacted a participant to a more than minimal extent and is related to the study activity must also be reported to the PHACS Regulatory and Compliance Manager by the study site through the QNS. Reportable events could involve study participants and/or staff members.

Examples of moderate and major impact events for study participants that could be related to the study activity include:

- Disruptive or violent behavior during the scheduled study visit session.
- Information regarding personal harm which is disclosed (e.g., current suicidal or homicidal ideation, physical or sexual abuse, active suicidal/homicidal intent, plan, and/or means).

- Significant visible distress or injury resulting from the research encounter (e.g., emotional response/distress as a result of responding to questions about violence, abuse, etc.).
- Breach of confidentiality.

Examples of moderate and major impact events for research staff that could be related to the study activity include:

- Inadequate preparation for management of research-related events.
- Visible distress or injury resulting from the research encounter.

Note: The distinguishing feature of moderate and major impact events is the need for enlisting additional support outside the research staff and the research encounter. The online surveys will include information on how and where participants can obtain assistance should they have feelings of anxiety, or other mental health concerns after completing the survey.

Examples of events for the community include:

- Any adverse community feedback received by the institution or the research team concerning the study.
- The study being portrayed adversely in any community forum or in the media.

The PHACS Regulatory and Compliance Manager will be responsible for reporting such events to the HLC IRB. The PHACS Regulatory and Compliance Manager will also work with the sites to ensure that the site's local IRB is notified of the event as required.

13.2.1 State Mandated Reporting Requirements

Laws governing the reporting of certain communicable diseases and illegal behaviors to authorities vary from state to state. Clinical sites are responsible for adhering to the reporting laws in their respective states. Clinical sites will consult with the HLC IRB and their local IRBs for guidance when needed.

13.3 Study Monitoring Plan

The ASTRO Standalone Study Protocol Team will hold regular conference calls to review study progress. These calls will occur at least monthly. More frequent calls or ad hoc calls may occur at the discretion of study's Protocol Chairs and Co-Chairs if a problem is identified that needs to be addressed immediately.

14. Statistical/Analytic Considerations

14.1 Sample Size

14.1.1 Study Sample

Data from the ASTRO Standalone Study (PH601) will be pooled with data from the ASTRO Nested Substudy of the TERBO BRAIN study (PH600) for analysis. The ASTRO Standalone Study and the ASTRO Nested Substudy will together enroll approximately 50 YAPHEU and 50 YAPHIV. The ratio between YAPHIV and YAPHEU will range from 1:1 up to 3:1 with maximum total enrollment of 110 individuals.

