4.6 Relationship with the ASTRO Nested Substudy

As a substudy of PHACS TERBO BRAIN the ASTRO Nested Substudy (PH601) engages youth and young adults enrolled in TERBO BRAIN to complete additional study procedures, specifically measurement of pulse wave velocity, fasting blood draw, and questionnaires. The ASTRO Standalone Study (PH601) has been initiated to augment recruitment of young adults to achieve our sample size goals (approximately 50 per YAPHIV and YAPHEU groups) for a pooled analysis.

**Aortic STiffness and ChRONic Comorbidities in Young Adults
with Perinatal HIV Infection or Exposure (ASTRO) Standalone Protocol (PH601)**

Participants in the ASTRO Standalone Study will undergo the same study procedures as the ASTRO Nested Substudy with a few modifications as specified in Section 7 and Appendix I.

5. Selection and Enrollment of ASTRO Standalone Study Participants

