Hypothesis 1b: Within YAPHIV and YAPHEU, the relationship of cfPWV with each metabolic and immune parameter (i.e., blood pressure, anthropometrics, serologic markers, and eicosanoids) will be plotted and categorizing the parameter will be considered if there is a deviation from a linear relationship. Unadjusted and adjusted linear regression models using GEE will be fitted to determine the association of each parameter with cfPWV. For analyses involving eicosanoids, a graphical lasso approach will be employed to estimate group-specific eicosanoid networks that are associated with cfPWV, as previously done [299]. Networks will be plotted using the R package igraph in which eicosanoids associated with cfPWV are represented as nodes and correlations between eicosanoids (conditional on all other analytes) are indicated by lines between nodes [300]. As an alternate approach, elastic net regression will also be considered in predictive modeling of all metabolic and immune parameters including eicosanoids.

Power calculations. Assuming a mean (SD) of 4.8 m/sec (0.97) in YAPHIV from preliminary data, there is 80% power to detect a difference of at least 0.55 m/sec of cfPWV between YAPHEU and YAPHIV ($\alpha = 0.05$, two-sided) and greater power in comparisons to individuals in the general population. For correlations within groups, there is 80% power to detect a correlation between cfPWV and each factor of interest of at least $r = 0.38$ within YAPHIV and YAPHEU ($\alpha = 0.05$). The minimum detectable correlation will be slightly higher when adjusted for confounders.

Expected Outcomes. In young adults, it is expected that aortic stiffness will be highest among YAPHIV, followed by YAPHEU, followed by individuals in the general population. It is also hypothesized that markers of metabolic and immune dysfunction (including eicosanoids) will directly relate to aortic stiffness within YAPHIV and YAPHEU.

14.2.2 Aim 2: To evaluate the role of aortic stiffness in the pathogenesis of neurocognitive dysfunction in individuals with PHIV and PHEU.

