In Aim 2, relationships of aortic stiffness with neurocognitive measures within YAPHIV and YAPHEU will be interrogated. Each group will be analyzed separately. Descriptive summaries will be prepared using the same approach described in Aim 1. Unadjusted and adjusted linear regression models will be fitted using GEE to assess associations between cfPWV and each neurocognitive parameter. A basic model will adjust for age, sex, race, and potential confounders (as listed in Aim 1). Analyses will be stratified by sex, obesity, and CRP to determine if key relationships differ by strata, acknowledging that these analyses will have limited power.

Power calculations. There is 80% power to detect a correlation of at least $r = 0.38$ within YAPHEU and YAPHIV unadjusted and a slightly higher correlation when adjusted ($\alpha = 0.05$).

Expected Outcomes. In YAPHIV and YAPHEU, cfPWV also will inversely relate to neurocognitive outcomes (e.g., Executive Function, Episodic/Working Memory, Fluid Cognition; NIH Toolbox).

15. Human Subjects

The ASTRO Standalone Study will be conducted in compliance with the protocol, International Council for Harmonisation of Technical Requirements for Pharmaceuticals for Human Use (ICH) GCP guidelines, and 45 CFR §46.

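### About 50 YAPHEU, a YAPHIV:YAPHEU ratio of up to 3:1 and a cap of 110 cannot all hold, and the 80% power statements describe only designs near 50 per group

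*Protocol*

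**What the plan says.** The synopsis, section 4.2 and section 14.1.1 of the protocol each give a pooled target of about 50 YAPHEU and about 50 YAPHIV across PH600 and PH601. Each also gives a permitted ratio and a ceiling; in section 14.1.1: "The ratio between YAPHIV and YAPHEU will range from 1:1 up to 3:1 with maximum total enrollment of 110 individuals". Section 4.6 repeats the goal as "approximately 50 per YAPHIV and YAPHEU groups". Sections 4.4 and 5.4 keep accrual open until the combined target sample sizes are reached. No minimum number of YAPHEU is set.

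The power paragraph of section 14.2.1 starts from "Assuming a mean (SD) of 4.8 m/sec (0.97) in YAPHIV from preliminary data" and states that "there is 80% power to detect a difference of at least 0.55 m/sec of cfPWV between YAPHEU and YAPHIV". For Hypothesis 1b it claims "80% power to detect a correlation between cfPWV and each factor of interest" of at least r = 0.38 within YAPHIV and within YAPHEU. Section 14.2.2 repeats this for Aim 2: "There is 80% power to detect a correlation of at least $r = 0.38$ within YAPHEU and YAPHIV unadjusted". Section 14.2.1 takes n of about 50 in each HIV group. No power figure is given for any unequal split. The only caveats are that adjusted detectable correlations will be slightly higher and that stratified analyses have limited power.

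**The concern.** The target, the ratio range and the cap sit in the same short paragraph but do not fit together. A study that uses the full permitted ratio ends with little more than half the planned YAPHEU, and would still be within the ratio and cap rules. The power statements would then describe a design other than the one carried out.

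This matters most for analyses within YAPHEU. Hypothesis 1b and Aim 2 are examined within each group, and section 14.2.2 analyses the groups separately, so extra YAPHIV participants cannot make up for missing YAPHEU. A reader of a null YAPHEU result would set it against an advertised 80% when the chance of detecting r = 0.38 was about one in two.

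There is also an operational loose end. If the targets are 50 per group, a study at or near 3:1 reaches 110 without ever meeting the closing condition in sections 4.4 and 5.4.

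**Working it through.** **Inputs.** From section 14.2.1: SD 0.97 m/sec (given for YAPHIV, taken here as common to both groups), difference 0.55 m/sec, r = 0.38, alpha 0.05. The document states two-sided for the difference; two-sided is assumed for the correlations. From section 14.1.1: about 50 per group, ratio 1:1 to 3:1, at most 110 in total. No loss to missing data is assumed.

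**Step 1: do the three limits fit?**
- 50 YAPHEU under the cap: 110 - 50 = 60 YAPHIV, so the largest ratio is 60/50 = 1.2:1.
- 50 YAPHEU at 3:1: 50 + 150 = 200 participants, well above 110.
- 3:1 under the cap: 110/4 = 27.5 YAPHEU. In whole numbers this is 81:27 (exactly 3:1, 108 in total) or 82:28 (2.93:1, 110 in total).

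**Step 2: reproduce the stated figures at 50:50.**
- Difference: SE = 0.97 × √(1/50 + 1/50) = 0.194. The ratio 0.55/0.194 = 2.835, and Φ(2.835 - 1.960) gives 80.9%. The noncentral t gives 80.2%, with a detectable difference of 0.549 m/sec. This matches 0.55.
- Correlation (Fisher z): atanh(0.38) × √(50 - 3) = 0.400 × 6.856 = 2.743, and Φ(2.743 - 1.960) gives 78.3%. Simulating the exact test gives 79.1%. The detectable r is tanh(2.8016/√47) = 0.387. This is close enough to 0.38.

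**Step 3: the same formulas across the permitted range.** The difference uses the noncentral t; the correlation uses Fisher z.

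| YAPHIV:YAPHEU | Ratio | Power for 0.55 m/sec | Detectable difference | YAPHEU power for r = 0.38 | YAPHEU detectable r |
|---|---|---|---|---|---|
| 50:50 | 1.0 | 80.2% | 0.549 | 78.3% | 0.387 |
| 60:50 | 1.2 | 83.5% | 0.525 | 78.3% | 0.387 |
| 66:44 | 1.5 | 82.3% | 0.534 | 72.6% | 0.412 |
| 73:37 | 1.97 | 79.5% | 0.553 | 64.5% | 0.447 |
| 82:28 | 2.93 | 72.8% | 0.600 | 51.6% | 0.508 |
| 81:27 | 3.0 | 71.5% | 0.609 | 50.0% | 0.517 |

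Example at n = 28: 0.400 × √25 = 2.000; Φ(2.000 - 1.960) = 51.6%; detectable r = tanh(2.8016/5) = 0.508.

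Within YAPHIV at n = 82, power for r = 0.38 is 94.5% and the detectable r is tanh(2.8016/√79) = 0.305; at n = 81 it is 0.307.

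**Step 4: adjusted correlations.** Section 14.2.1 names age, sex and race, and gives caregiver education, adverse childhood experiences and physical activity as examples of further confounders. Assuming one term each, six in all, the detectable r is tanh(2.8016/√(n - 3 - 6)):
- n = 50: tanh(2.8016/√41) = 0.41
- n = 28: tanh(2.8016/√19) = 0.57
- n = 27: tanh(2.8016/√18) = 0.58

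**The case against.** The strongest defence is that the stated figures are right for the sample they assume, that the group sizes are worded as approximate targets, and that 3:1 is only the far end of a range in a study that calls itself a pilot. Much of this stands. The 50:50 figures reproduce. With 110 enrolled, the 0.55 m/sec claim survives to about 2:1, and its worst loss is 7 to 9 points. YAPHIV gains power as the ratio rises. What does not stand is that loose wording covers the gap: 27 or 28 is not approximately 50, and the 80% claims are made for YAPHEU without qualification.

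Three stronger readings are tempting and are not supported.
- A reader might apply 3:1 to a total of 100 and conclude that 25 YAPHEU is a compliant outcome. Stopping there falls short of the YAPHEU target while room remains under the cap, which goes against the accrual rule in sections 4.4 and 5.4. Only the case at the cap is supportable.
- A reader might say that YAPHEU analyses lose half their advertised power. The absolute power is about one half; relative to 80% it is 0.50/0.80 to 0.516/0.80, or about 63-65%.
- A reader might also attack the claim of "greater power in comparisons to individuals in the general population", because the roughly 450 comparators are weighted and their effective number is smaller. The protocol gives no covariate distributions from which to compute that number, so no error in that sentence can be shown.

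**Conclusion.** The point holds as an internal contradiction with a measurable effect on the power statements. The target of about 50 YAPHEU is compatible with the cap only up to 1.2:1, while the protocol permits 3:1. For the comparison between groups the consequence is moderate and appears only beyond about 2:1. For correlations within YAPHEU it is already visible at 1.5:1 and large at 3:1. The error lies in presenting one set of figures for a range of designs, not in the 50:50 calculation itself.

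The result rests on a common SD of 0.97, two-sided tests, full enrolment to the cap and complete data. Refused or missing assessments, which section 7 allows, would lower the YAPHEU figures further. The adjusted values also depend on the assumed six covariate terms. Target, ratio, cap and power are all fixed in the protocol, so this is not a detail left to a statistical analysis plan.

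**What to change.** Keep the permitted range and, in the power paragraphs of sections 14.2.1 and 14.2.2, give the detectable effects at the 3:1/110 extreme beside the 50:50 figures:
- between groups, 0.60-0.61 m/sec;
- within YAPHEU, r of about 0.51-0.52 unadjusted, and about 0.57-0.58 adjusted if six covariate terms are assumed;
- within YAPHIV, r of about 0.31 unadjusted, somewhat higher adjusted.

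State that the 0.55 m/sec and r = 0.38 figures apply at about 50 per group. Reconcile sections 4.4 and 5.4 with the cap, so that it is clear when accrual closes if 110 is reached before 50 YAPHEU are enrolled.

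If recruitment allows, the sponsor may instead state a minimum YAPHEU number or a narrower ratio consistent with about 50 YAPHEU. That restricts recruitment, and its feasibility cannot be judged from the protocol, so it is an option and not a requirement.

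The main fix changes wording only. Its price is that the stated detectable effects look less favourable. It needs no extra participants.

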14.1.2 Comparison Participants

Similar-age individuals from the general population ($n \approx 450$) from the repository of cfPWV data that had been previously curated by [name] will be used as comparison groups.

14.2 Statistical Analyses

Analyses described below are for pooled data from the ASTRO Standalone Study and the ASTRO Nested Substudy.

14.2.1 Aim 1: To investigate the impact of in utero HIV exposure and perinatal HIV infection on aortic stiffness in young adults

In Aim 1, differences in cfPWV between groups will be assessed, and relationships of cfPWV with metabolic and inflammatory parameters within each group will be examined. YAPHIV ($n \approx 50$), YAPHEU ($n \approx 50$), and young adults from the general population ($n \approx 450$) will be compared.

To minimize differences between groups, the general population sample will be standardized to the combined group of YAPHIV and YAPHEU on key covariates using probability weighting [289]. A propensity score for each participant will be obtained using a logistic regression model with study group (combined YAPHIV and YAPHEU, general population) treated as the outcome and rounded age, sex, race, and BMI treated as predictors. All YAPHEU and YAPHIV will be given a weight of 1, whereas the weight for each individual in the general population will be defined as (propensity score)/(1 - propensity score). A sensitivity analysis in which the general population sample is standardized to YAPHIV or YAPHEU individually and compared to each group in separate analyses will also be performed.

For analyses, variables that are not normally distributed and right-skewed will be log-transformed to approximate a normal distribution. **Hypothesis 1a:** The distribution of sociodemographic and clinical variables (including cfPWV) will be described across study groups using the mean (standard deviation, SD) and frequency, as appropriate, before and after weighting. To compare cfPWV between groups, unadjusted and adjusted linear regression models with weighting will be fit using generalized estimating equations (GEE) to obtain the robust variance estimator. The average difference (95% confidence interval, CI) will be reported for each pair of groups. The basic adjusted model will include age, sex, race, and potential confounders (e.g., primary caregiver education [290-292], adverse childhood experiences [293-295], and physical activity [296-298]). Analyses stratified by sex and obesity will also be performed to evaluate qualitatively whether differences in cfPWV between groups differ by strata, acknowledging that these analyses will have limited power.

Hypothesis 1b: Within YAPHIV and YAPHEU, the relationship of cfPWV with each metabolic and immune parameter (i.e., blood pressure, anthropometrics, serologic markers, and eicosanoids) will be plotted and categorizing the parameter will be considered if there is a deviation from a linear relationship. Unadjusted and adjusted linear regression models using GEE will be fitted to determine the association of each parameter with cfPWV. For analyses involving eicosanoids, a graphical lasso approach will be employed to estimate group-specific eicosanoid networks that are associated with cfPWV, as previously done [299]. Networks will be plotted using the R package igraph in which eicosanoids associated with cfPWV are represented as nodes and correlations between eicosanoids (conditional on all other analytes) are indicated by lines between nodes [300]. As an alternate approach, elastic net regression will also be considered in predictive modeling of all metabolic and immune parameters including eicosanoids.

Power calculations. Assuming a mean (SD) of 4.8 m/sec (0.97) in YAPHIV from preliminary data, there is 80% power to detect a difference of at least 0.55 m/sec of cfPWV between YAPHEU and YAPHIV ($\alpha = 0.05$, two-sided) and greater power in comparisons to individuals in the general population. For correlations within groups, there is 80% power to detect a correlation between cfPWV and each factor of interest of at least $r = 0.38$ within YAPHIV and YAPHEU ($\alpha = 0.05$). The minimum detectable correlation will be slightly higher when adjusted for confounders.

Expected Outcomes. In young adults, it is expected that aortic stiffness will be highest among YAPHIV, followed by YAPHEU, followed by individuals in the general population. It is also hypothesized that markers of metabolic and immune dysfunction (including eicosanoids) will directly relate to aortic stiffness within YAPHIV and YAPHEU.

14.2.2 Aim 2: To evaluate the role of aortic stiffness in the pathogenesis of neurocognitive dysfunction in individuals with PHIV and PHEU.

In Aim 2, relationships of aortic stiffness with neurocognitive measures within YAPHIV and YAPHEU will be interrogated. Each group will be analyzed separately. Descriptive summaries will be prepared using the same approach described in Aim 1. Unadjusted and adjusted linear regression models will be fitted using GEE to assess associations between cfPWV and each neurocognitive parameter. A basic model will adjust for age, sex, race, and potential confounders (as listed in Aim 1). Analyses will be stratified by sex, obesity, and CRP to determine if key relationships differ by strata, acknowledging that these analyses will have limited power.

Power calculations. There is 80% power to detect a correlation of at least $r = 0.38$ within YAPHEU and YAPHIV unadjusted and a slightly higher correlation when adjusted ($\alpha = 0.05$).

Expected Outcomes. In YAPHIV and YAPHEU, cfPWV also will inversely relate to neurocognitive outcomes (e.g., Executive Function, Episodic/Working Memory, Fluid Cognition; NIH Toolbox).

15. Human Subjects

The ASTRO Standalone Study will be conducted in compliance with the protocol, International Council for Harmonisation of Technical Requirements for Pharmaceuticals for Human Use (ICH) GCP guidelines, and 45 CFR §46.

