7.5.2 Eicosanoid Profiling

Fasting blood will be drawn for eicosanoid profiling. Eicosanoid profiling (>100 eicosanoids) will be performed on fasting plasma samples using semi-targeted metabolomics techniques in the Einstein Stable Isotopes and Metabolomics Core under the direction of [name], PhD. Samples will be processed, stored locally, and shipped to the PHACS Repository as specified in the ASTRO Standalone Study LPC. Eicosanoids are a complex network of bioactive lipids that play critical roles in biologic processes including metabolism, inflammation, and endothelial function [236]. In collaboration with [name], we have previously shown a distinct eicosanoid signature in infants with PHEU vs. controls in association with metabolic and immune parameters [148]. In the general population, plasma eicosanoids have been shown to strongly correlate with blood pressure [237], which is mechanistically linked to arterial stiffness [141]. Furthermore, supplementation of omega-3 polyunsaturated fatty acids (key eicosanoid precursors) has been found to attenuate arterial stiffness in several small studies [160], possibly due to a favorable shift in the eicosanoid profile [238]. In this study, relationships of eicosanoids with aortic stiffness among the PHIV and PHEU populations will be investigated. Evidence of novel associations between eicosanoids and aortic stiffness may implicate omega-3 fatty acid supplementation as a potential intervention to attenuate aortic stiffness in these groups, to be explored in future studies.

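### Per-factor alpha of 0.05 and the 80% power at r = 0.38 are applied to a screen of more than 100 eicosanoids in each of two groups, though they hold only for one unadjusted test

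*Protocol*

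**What the plan says.** Section 14.2.1 (Hypothesis 1b) examines cfPWV against "each metabolic and immune parameter (i.e., blood pressure, anthropometrics, serologic markers, and eicosanoids". For these it says: "Unadjusted and adjusted linear regression models using GEE will be fitted to determine the association of each parameter with cfPWV". The introduction to Aim 1 in the same section says that "relationships of cfPWV with metabolic and inflammatory parameters within each group will be examined", so YAPHIV and YAPHEU are each analysed, at about 50 participants per group. Section 7.5.2 gives the size of the panel: "Eicosanoid profiling (>100 eicosanoids) will be performed on fasting plasma samples".

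The power paragraph of Section 14.2.1 claims "80% power to detect a correlation between cfPWV and each factor of interest" of at least 0.38 within each group at alpha 0.05. It qualifies this figure only for confounder adjustment, not for the number of factors.

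For eicosanoids the protocol also plans a graphical lasso network in each group and may use elastic net. The network plot shows as nodes those eicosanoids that are associated with cfPWV, but no rule for being associated is given. False discovery rate appears in the abbreviation list, and a paper on it appears in the reference list, but no sentence of Section 14.2 uses either.

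**The concern.** A per-test alpha and a per-test detectable correlation suit a short list of prespecified markers. Here the same figures cover a screen of at least 200 single-parameter associations (more than 100 eicosanoids in two groups). Two things follow.

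First, if p < 0.05 were used to call an eicosanoid associated, several chance associations would be expected even if none is real, and nothing in the text separates them from true ones.

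Second, the power statement tells the reader that an eicosanoid with r = 0.38 has an 80% chance of detection. That cannot remain true once any multiplicity control is applied. A reader using the protocol to judge what the eicosanoid work can show would be misled about the size of effect it can reliably find.

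**Working it through.** **Inputs.** Eicosanoids: more than 100, with 100 used as the lower bound (Section 7.5.2). Groups: 2, n about 50 each (Section 14.2.1). Alpha 0.05, power 80%, r = 0.38 (Section 14.2.1, power calculations). Alpha is taken as two-sided; the protocol does not say so for the correlations.

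**1. The protocol's own figure.** Fisher z: r = tanh((z(1−α/2) + z(0.80)) / √(n−3)).
- (1.960 + 0.842) / √47 = 2.802 / 6.856 = 0.409; tanh(0.409) = 0.387.
- Power at r = 0.38: Φ(atanh(0.38) × 6.856 − 1.960) = Φ(2.743 − 1.960) = 78%. A simulated t-test of r gives 79%.

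The stated r = 0.38 therefore reproduces, to rounding, for one unadjusted test.

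**2. Expected chance findings at p < 0.05.**
- No eicosanoid related to cfPWV: 100 × 0.05 = 5 per group; 2 × 5 = 10 overall.
- Adding an assumed 10 to 20 other markers: 2 × 110 × 0.05 = 11 to 2 × 120 × 0.05 = 12.
- If 10% to 30% of the eicosanoids are truly related: 2 × 90 × 0.05 = 9 down to 2 × 70 × 0.05 = 7 false findings.
- At n = 50, p < 0.05 needs only |r| of about 0.28.

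**3. Effect of correlation among eicosanoids.** Simulated null data, 100 analytes, two groups of 50, common correlation assumed:

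| Common correlation | Mean count | Median | 95% range | At least one |
|---|---|---|---|---|
| 0 | 9.9 | 10 | 4 to 16 | >99% |
| 0.3 | 10.1 | 8 | 2 to 31 | >99% |
| 0.6 | 10.1 | 4 | 0 to 52 | 88% |

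The mean stays at 10, apart from simulation error; the realised count may be near zero or far above it.

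**4. Detectable r and power once error is controlled (n = 50).**
- Bonferroni over 100 tests in one group: α = 0.05/100 = 0.0005, z = 3.481. r = tanh((3.481 + 0.842)/6.856) = tanh(0.630) = 0.56. Power at r = 0.38: Φ(2.743 − 3.481) = 23%.
- False discovery rate of 5%, large-sample approximation: with t true associations of r = 0.38 among 100, find the threshold a for which 100a / (t × power(a) + (100 − t)a) = 0.05.

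| True associations (t) | Threshold a | Average power at r = 0.38 | Detectable r |
|---|---|---|---|
| 5 | 0.0007 | 25% | 0.55 |
| 10 | 0.0019 | 36% | 0.52 |
| 20 | 0.0049 | 47% | 0.49 |

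All three lie between the Bonferroni result (23%, r = 0.56) and the uncorrected one (78%, r = 0.39).

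**The case against.** The strongest reply is that multiplicity handling for a biomarker screen is commonly left to the SAP, which is not shown. Alpha 0.05 appears only as a planning level, and no sentence makes p < 0.05 the rule for declaring an eicosanoid. This stands: the protocol's silence is not a decision against error control. It does not rescue the power statement. If the SAP controls error, the r = 0.38 claim does not apply to the eicosanoids; if it does not, about 10 chance findings are expected under the null. The text needs correcting either way.

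It can also be said that r = 0.38 is a per-factor figure and is right as such. That is true for the named markers taken singly. The wording extends it to every factor, and the factors expressly include the eicosanoids.

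Three stronger readings are tempting, and the documents do not support them.
- A reader might infer that false positives are bound to enter the eicosanoid networks. The protocol does not say that single-parameter p-values choose the nodes, and it names penalised joint methods as well. The link is possible because the node rule is unstated, but it is an inference.
- A reader might infer that the study will make intervention claims from these hits. Section 7.5.2 says only that associations "may implicate omega-3 fatty acid supplementation as a potential intervention", to be pursued in later studies, and Section 2.2 calls this a pilot.
- A reader might suppose that small-sample error in the robust variance doubles or triples the count. That is a separate question, depends on whether a correction is used, and is not part of this point.

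**Conclusion.** The point holds in limited form. The protocol applies a single-test alpha and a single-test power figure to a family of more than 100 analytes in each of two groups. The expected 10 chance associations are a mean under the assumption that no eicosanoid is related to cfPWV and that p < 0.05 is used; they are not a predicted yield. For the eicosanoids, the detectable correlation at n of about 50 is roughly 0.49 to 0.56 under the controls examined, not 0.38, and power at r = 0.38 is roughly 23% to 47%, not 80%. Bonferroni is the strictest of these and is shown as a bound, not as the recommended method. The false discovery figures rest on an assumed 5 to 20 true associations, all of size 0.38. All figures are for unadjusted correlations at about 50 per group; the protocol itself notes that covariate adjustment raises the detectable r.

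**What to change.** In Section 14.2.1:
1. Name blood pressure, anthropometrics and the serologic markers of Section 7.5.1 as the hypothesis-driven family, and treat the eicosanoids as a separate screen.
2. Apply Benjamini-Hochberg control, at a stated level, across the eicosanoid regressions within each group and within each model (unadjusted, adjusted).
3. State the rule by which an eicosanoid counts as associated with cfPWV for the network plot.
4. Say that r = 0.38 applies to a single unadjusted test, and give the multiplicity-controlled range for eicosanoids beside it.

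The cost is a few lines of text, with no new data, participants or procedures. The downside is real: fewer eicosanoids will be declared, and the detectable r stated for them will be less favourable.
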